### **14.3 Early Termination of the Study**

The study may be terminated prematurely by the principal investigator or his/her designee and the sponsor if:

- The number and/or severity of adverse events justify discontinuation of the study
- New data become available which raise concern about the safety of the study treatment, so that continuation might cause unacceptable discomfort to participants.

In addition the sponsor reserves the right to discontinue the trial prior to inclusion of the intended number of participants, but intends only to exercise this right for valid scientific or administrative reasons.

After such a decision, the investigator must contact all participating participants within two weeks, and written notification must be sent to the Ethics Committee.

## **15 Electronic Case Report Form (eCRF)**

An electronic Case Report Form (eCRF) will be completed for each study participant summarising all clinical screening and study data. Participants will only be referred to in the eCRF by their participant number and initials in order to retain participant confidentiality.

The completed eCRFs will be submitted to the Sponsor as soon as practical after completion and review. A copy of each completed eCRF will be printed and retained by the investigator at the recruiting site for at least 7 years from the end of the study and according to local regulations.

All data entered on the eCRF will have supporting source data located at the study site in the participant's research record. Data allowed to be recorded directly in to the eCRF (i.e. no prior written or electronic record of data), will be discussed and documented with the Sponsor at the commencement of the trial.

## 16 Data Analysis and Statistical Considerations

### 16.1 Hypotheses

#### *Primary hypothesis*

H1 Compared to usual care, implementation of the proposed intervention package (IP) will result in an at least 15 point higher score on the Euro QOL–5D-3L VAS at 26 weeks post injury

#### *Secondary hypotheses:*

H2a Compared to usual care, implementation of the IP will result in significant improvement in service delivery at 12 and 26 weeks post injury as related to increased occasions of service

H2b Compared to usual care, implementation of the IP will result in significant improvement in service delivery at 12 and 26 weeks post injury as related to increased compliance with minimum process of care indicators

H3 Compared to usual care, implementation of the IP will result in significant improvement in neurological disability (Modified Rankin Scale) and independence (Functional Independence Measure) at 12 and 26 weeks post injury

H4 Compared to usual care, implementation of the IP will result in significantly reduced carer burden (Modified Caregiver Strain Index) and less brain injury survivor anxiety and depression (Hospital Anxiety and Depression Scale) at 12 and 26 weeks post injury

H5 The culturally sensitive IP will be more cost-effective (additional benefits gained will justify additional costs for delivering the intervention; may lead to potential cost-offsets from less severe disease) than usual care at 12 and 26 weeks post injury.

H6 The IP will be acceptable to health professionals and Aboriginal participants and their families, and the role of the Aboriginal Brain Injury Coordinator a feasible one.

### 16.2 Outcome Measures

Data collection point (Time post injury)	Baseline (0-4 wks)	1 (12wks)	2 (26wks)
Demographic data	X		
Injury data	X		
Site Usual Care data		X	X
Modified Caregiver Strain Index		X	X
mRS	X	X	X
FIM™	X	X	X
HADS	X	X	X
EuroQoL-5D-3L		X	X
Resource Utilisation		X	X
Process of care indicators		X	X
Participant satisfaction		X	X
Staff satisfaction	X		

### 16.2.1 Primary Outcome Measure

The *Primary outcome measure* is the Euro QoL–5D-3L which will be administered at 6 months post symptom onset. It is hypothesised that in improving rehabilitation service delivery in terms of culturally secure practices, that health outcomes will also be improved for Aboriginal people. While the service delivery aim is the obvious prerequisite aim in this context, a QoL measure was chosen as the primary outcome measure, as improvement in general QoL is the ultimate goal of rehabilitation, rather than simply improvement in service delivery. The notion of QoL captures a more holistic picture of outcome, consistent with an Aboriginal view of health and is more meaningful than simply an impairment-based outcome. The EQ-5D, developed by the Euroquol group, measures the health-related dimensions of mobility, self-care, usual activities, pain/discomfort, and anxiety/depression. It has been used with stroke and traumatic brain injury survivors, validated in many different countries and cultural settings, and can be administered by face to face or telephone interview, or as a self-or proxy mail out. It is used in the Australian Stroke Clinical Registry, as well as other stroke registries, hence can be used for international comparison.

### 16.2.2 Secondary Outcome Measures

These relate to the further health outcomes of stroke severity (modified Rankin Score), functional independence (Functional Independence Measure -FIM™), burden of care (Modified Caregiver Strain Index), anxiety and depression (Hospital Anxiety and Depression Scale) and clinical service provision (Minimum Process of Care Indicators). Clinical service provision will be recorded for the six month period following patient admission. Data collected will include inpatient rehabilitation related sessions and out-patient service use up to six months post onset (rehabilitation specialist, allied health sessions), place where services are provided, including allied health/medical specialists visiting patients in their homes/remote communities. All constitute contributors to QoL and as such are important components for study. As part of a process evaluation, participant satisfaction will be measured through questionnaires administered either face to face or by phone/telehealth facility. Staff satisfaction

will be measured through questionnaires administered both face to face and online.

### **16.3 Sample Size**

Sample size was estimated using GPower 3.1, and adjusted for the design effect of the stepped-wedge design using the method described in Woertman et al. Based on the literature, the mean difference between stroke and non-stroke populations on the Euro QOL–5D VAS is approximately 25 points with a standard deviation of 25. We anticipate that the intervention will result in an improvement of 15 points on the Euro QOL–5D VAS (with a standard deviation 25). This equates to a medium-large effect size of  $d=0.6$ . GPower estimated that we would require a total of 90 participants to detect this difference with 80% power at the 5% significance level. To adjust for the design effect, we assumed a conservative intraclass correlation of 0.08. After adjusting for the design effect for a 4-step stepped-wedge design with one baseline measurement and one follow-up measurement, we estimate that we will need to recruit 13 patients at each site in every time period. This equates to a total sample size of 312 patients.

### **16.4 Statistical Analyses**

The primary analysis will be performed on an intention to treat basis with each participant allocated to the site at which he/she was originally recruited.

#### **16.4.1 Primary outcome analysis**

The primary hypothesis (H1) will be analysed using a mixed effects linear regression model, which controls for the effects of secular trends over time. The model will be designed to assess the effect of the intervention on Euro QOL–5D-3L VAS score at 26 weeks post injury. Differences in baseline characteristics will be included in the model.

#### **16.4.2 Secondary outcomes analyses**

A mixed effects logistic regression model will be used to assess the impact of the intervention on the odds of achievement of the minimum processes of care [H2a]. The outcome variable will be a binary variable: minimum processes of care received by patient in the first 26 weeks post brain injury versus minimum processes of care not received by patient in the first 26 weeks post brain injury. Time will be included as a fixed effect in the model to control for the effects of secular trends. Site will be included as a random effect in the model.

A linear mixed effects regression model will be used to assess the impact of the intervention on the occasions of service [H2b]. The outcome variable will be the count of the occasions of service in the first six months post brain injury. Type and severity of the brain injury will be controlled for in the model. Time will be included as a fixed effect in the model to control for the effects of secular trends. Site will be included as a random effect in the model.

To examine the secondary outcomes of effects of the intervention on stroke/TBI disability and independence after injury [H3], the mRS score will be dichotomised into good outcome (mRS 0-2) and poor outcome (mRS 3-6). A logistic generalized linear mixed model will be developed to assess the impact

of the intervention on mRS at baseline, 12 and 26 weeks after injury. Within-cluster effects will be controlled for in the model and deviations from the protocol caused by changes in care site will be included as random effects.

A longitudinal linear mixed model will be used to assess the impact of the intervention on carer burden [H4]. The outcome variable will be the Modified Caregiver Strain Index at 12 and 26 weeks post brain injury. Type and severity of the brain injury will be controlled for in the model. Time period will be included as a fixed effect in the model to control for the effects of secular trends. Site will be included as a random effect in the model.

A longitudinal linear mixed model will be used to assess the impact of the intervention on anxiety and depression [H4]. The outcome variable will be the Hospital Anxiety and Depression Scale at 12 and 26 weeks post brain injury. Type and severity of the brain injury will be controlled for in the model. Time period will be included as a fixed effect in the model to control for the effects of secular trends. Site will be included as a random effect in the model.

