### **10.2 Participant Assessment Schedule**

#### **10.2.1 Baseline Assessments**

Assessors trained in the use of all assessment tools will collect all patient related data. Required study assessments are outlined in Appendix 1 – Schedule of Assessments.

Individual baseline data will preferably be collected on the same day as consent (or within 2 days if recruited over a weekend) from participants who meet all inclusion criteria and have provided consent. The assessment will be completed within 42 days of injury. The assessments completed at baseline will be: modified Rankin Score (mRS), Functional Independence Measure (FIMTM), Hospital Anxiety Depression Scale.

Baseline data collection will include the collection and documentation of:

- 1) Demographic details including age, gender, languages spoken, language group, residence location (metro/rural/remote), premorbid employment, Aboriginal or Torres Strait Islander status, living arrangements at the time of admission
- 2) Details related to brain injury type (stroke vs traumatic brain injury), and pathological sub-types of each (stroke: ischaemic vs haemorrhagic; TBI: closed, penetrating, blast, crush - as per IMPACT core data set), hemisphere(s) involved, first or recurrent/subsequent injury, and severity as determined by the National Institutes of Health Stroke Scale (for the post stroke participants) and the Glasgow Coma Scale (for the post traumatic brain injury participants). Cause of the TBI i.e. road traffic incident vs violence will also be recorded.
- 3) Past medical history, brain injury history and comorbidities.
- 4) The assessment tasks should be completed in a single session. If the participant is unable to complete assessment tasks in a single session, they must be completed on the same day if possible (i.e. over a morning and afternoon session). If this is not possible, the assessments should take place on consecutive days. Protocol deviations will be recorded if assessment sessions are not completed on the same day or if sessions are completed later than the due date +/- 7 days.

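### The process-of-care and mRS models leave out injury type and severity, and the mRS model names no calendar-time term, unlike the other three secondary models

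*Protocol*

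**What the plan says.** Section 16.4.2 of the protocol sets the terms of five secondary models one by one. They are named here by outcome, because the H2a and H2b labels in that section do not match those in section 4.2.

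| Outcome | Type and severity | Calendar time | Site or cluster |
|---|---|---|---|
| Process of care (logistic) | not named | fixed | site, random |
| Occasions of service | named | fixed | site, random |
| mRS 0-2 v 3-6 (logistic) | not named | not named | within-cluster effects; changes of care site, random |
| Carer strain | named | fixed | site, random |
| HADS | named | fixed | site, random |

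The process-of-care model is to "assess the impact of the intervention on the odds of achievement of the minimum processes of care". For each of the three adjusted outcomes the text says "Type and severity of the brain injury will be controlled for in the model".

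The covariates exist. Section 10.2.1 records injury type (stroke or TBI) and "severity as determined by the National Institutes of Health Stroke Scale" for stroke, with the Glasgow Coma Scale for TBI. The primary model (16.4.1) controls for secular trend and includes baseline characteristics.

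**The concern.** Two things are at stake.

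**Power.** In a logistic model, leaving out a prognostic covariate pulls the odds ratio towards 1 and costs power.

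**Bias.** Patients are recruited one by one, after their site's phase is known. The blinding paragraph of 16.4.2 concedes that assessors, patients and most investigators cannot be blinded. One inclusion criterion (7.2.1) is the local team's judgement of ability to benefit from rehabilitation. The severity mix could therefore change when a site switches. Such a change coincides exactly with the treatment indicator, so site and period terms cannot absorb it; only patient-level covariates can. In the mRS model, with no period term named, even a drift shared by all sites is partly credited to the intervention, because intervention time falls late in the trial.

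**Working it through.** **The plan's own figure.** Section 16.3 says "GPower estimated that we would require a total of 90 participants to detect this difference with 80% power at the 5% significance level". A two-sided t-test with d = 15/25 = 0.6 needs 45 per arm, so 90 in total (power 80.4%). With "we assumed a conservative intraclass correlation of 0.08", four steps, one baseline and one follow-up measurement, and 13 per cluster-period, the stepped-wedge design effect is 0.557. Then 90 x 0.557 = 50.2, and 50.2/13 = 3.86, so 4 clusters (pairs of sites). Over the 6 half-years of Figure 1, 4 x 13 x 6 = 312. These figures concern the primary outcome. They supply the layout but no power for process of care or mRS.

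**Layout used.** 312 patients, 8 sites, 6 periods, with pairs switching after periods 1, 2, 3 and 4. Pair-periods under intervention: 5 + 4 + 3 + 2 = 14 of 24, so 312 x 14/24 = 182 patients.

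**Assumptions, none given in the protocol.** Event rate about 50%; intervention odds ratio about 3 (d = 0.6 converts to 0.6 x pi/sqrt(3) = 1.09 on the log scale, OR 2.97, borrowed from the EQ VAS); severity effect b per SD on the log-odds scale, varied. The runs used logistic regression with site and period terms, fitted with and without the covariates.

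**Power without and with the covariates.**

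| Intervention OR held at 3 | b | Without | With |
|---|---|---|---|
| in the adjusted model | 0.41 (OR 1.5 per SD) | 63% | 65% |
| in the adjusted model | 0.69 (OR 2) | 60% | 63% |
| in the adjusted model | 1.10 (OR 3) | 52% | 60% |
| in the unadjusted model | 0.4 | 69-70% | 71% |
| in the unadjusted model | 0.8 | 68-75% | 74-79% |
| in the unadjusted model | 1.2 | 62-66% | 76-78% |
| in the unadjusted model | 1.5 | 65% | 75% |

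The first three rows come from 1,500 runs each and adjust for type (one third TBI) and severity. The rest come from runs of 600 to 3,000 and adjust for severity alone; a range means that runs were repeated. Gains run from about 1 to 14 points. They are larger in the lower rows because fixing the unadjusted OR at 3 implies a larger adjusted effect.

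**False effect when severity shifts by s SD at each site's own switch, with no true effect.** A hand check is log OR = b x s / sqrt(1 + 0.346 b^2), the usual logistic-normal attenuation.

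| b | s | Formula | OR by formula | OR simulated | False positives, unadjusted |
|---|---|---|---|---|---|
| 0.4 | 0.4 | 0.16/1.027 = 0.156 | 1.17 | about 1.2 | 7% |
| 0.69 | 0.25 | 0.173/1.080 = 0.160 | 1.17 | about 1.2 | 8% |
| 0.69 | 0.5 | 0.347/1.080 = 0.321 | 1.38 | 1.41 | 14% |
| 0.69 | 1.0 | 0.693/1.080 = 0.642 | 1.90 | 1.94 | 31% |
| 1.2 | 0.4 | 0.48/1.224 = 0.392 | 1.48 | 1.46-1.50 | 15% |

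At b = 1.2, shifts of 0.1 and 0.2 SD gave 5% and 7%. With no shift, the unadjusted rate was 5.9%. With adjustment, the OR returned to about 1 and the rate to 5-7%. Monte Carlo error near 5% is sqrt(0.05 x 0.95/1500) = 0.6 points.

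**Drift not aligned with the switch (b = 0.69).** A 0.5 SD drift common to all sites gave 5% false positives with period in the model and 11% without it (log OR 0.18). Random site-specific drift gave 5.5-6%.

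**The case against.** **Covariate lists often belong in the SAP, which is not shown.** True in general. The mRS model is also described as still to be developed, and nowhere does the protocol say that type and severity will be excluded. But this section does not leave covariates open: it names them for three models and not for two. What stands is an unexplained inconsistency, not an error of method.

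**Severity may matter little for process of care.** Indicators in 10.4 such as language noted in the file or liaison officer involvement need not depend strongly on severity. This stands. At b = 0.4 the gain is 1 to 2 points, and a 0.4 SD shift gives only 7% false positives.

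**The simulation is not the mRS model.** This also stands. It has one outcome per patient, whereas the mRS model is longitudinal and takes baseline mRS as one of its outcomes. That may carry some severity information, though not injury type. For mRS the figures show direction only.

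**Stronger readings that the documents do not support.**
- A reader might infer that NIHSS and GCS, which run in opposite directions, will enter as one pooled term. No such coding is stated; 10.2.1 defines severity by injury type.
- A reader might want severity taken from admission records. Appendix 1 assigns both scores to the trained baseline assessor, and the file audit in 10.4 lists neither.
- A reader might call for residence location as well. No secondary model names it, so there is no inconsistency to correct, and no calculation supports it.

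**Conclusion.** The point holds as a low-cost improvement to two secondary analyses. The primary analysis is not touched, and neither is occasions of service, the other service-delivery outcome.

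The power loss is about 1 to 14 points, depending on the assumed prognostic strength. With an assumed switch-aligned shift of 0.4 to 0.5 SD, the false odds ratio is about 1.2 to 1.5 with 7 to 15% false positives. Such a shift is plausible given open site phase and a judgement-based criterion, but nothing shows that it will occur. The planned baseline comparison between conditions could reveal it but would not correct for it.

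It would be wrong to conclude that any case-mix drift biases the process-of-care result: its time term already removes drift common to all sites. The mRS model as worded lacks that protection.

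**What to change.** In 16.4.2:

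- **Process-of-care model:** add injury type, and severity within type, as fixed effects.
- **mRS model:** add the same terms, and time period as a fixed effect, as in the other secondary models. Both additions are needed: severity adjustment deals with drift in case mix, and the period term with drift in care.
- **Severity within type** means one slope for NIHSS among stroke participants and one for GCS among TBI participants, using the scores collected under 10.2.1.

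If the omission was deliberate, state the reason instead. The cost is three parameters in each model (type and two slopes), five period terms in the mRS model (six periods less one) and a few lines of text, to be settled before outcome data are seen. No patients, visits or measurements are added.

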## 2 Protocol Synopsis

Study Title:	Enhancing rehabilitation services for Aboriginal Australians after brain injury.
Protocol Number:	ECU 2017
Trial Registration	TBA
Development Phase:	Phase 3
Indication:	Aboriginal Patients following brain injury
Study Intervention	
The intervention consists of two components:
 
i) Cultural Security Training for hospital staff surrounding brain injury, including culturally appropriate educational and treatment resources,
 
ii) The introduction of an Aboriginal Brain Injury Coordinator at each site. The Coordinator will see the participants in hospital and up till 26 weeks post injury, providing education, support, liaison, and advocacy services to the participants and their families.
 
A stepped wedge cluster randomised control trial (CRCT) design will be used, with individual healthcare sites functioning as clusters. Twenty-six weeks of baseline control data will be obtained prior to implementation of the intervention, which will be introduced sequentially to all sites at 26-week intervals. Sites will be randomised at the beginning of the project to determine the sequencing of the introduction of the intervention period.

Total number of Participants:	312
No. Centres:	Eight acute care hospitals (4 metropolitan and 4 regional) will participate in the study.
Study Duration:	Anticipated recruitment over 4 years Participant involvement is 26 weeks duration
Objectives of the Study:	
Objectives are to:
 
 
1. improve delivery of rehabilitation services to Aboriginal people post-brain injury (stroke and
 

	
traumatic brain injury)
 
 
2. improve overall health outcomes for the above population
 
3. conduct an economic evaluation to support the business case for funding new rehabilitation services which will contribute to the planning and sustainability of future services if the Intervention is determined to be cost-effective
 
4. explore the acceptability of the intervention from the perspectives of the health professionals and the Aboriginal participants involved, and to utilise this information to assist in interpretation and translation of findings
 

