## **10.4 Service data**

Site data will be collected with respect to services delivered to each participant for six months during the control and intervention periods. This data will consist of:

- Occasions of service per allied health discipline (Physiotherapy, Occupational Therapy, Speech Pathology, Social Work, Dietetics; Clinical Psychology/ Neuropsychology; Prosthetics/Orthotics; Therapy Assistant; inpatient and outpatient)

The data will be collected through a medical file review process and through access to hospital administrative data systems as needed.

In addition, *Minimum Process of Care Indicators* will capture data on whether key processes of care occurred while the patient was in hospital and/or within 26 weeks of injury.

The data collection will:

- involve extraction of relevant data from medical file (audit process)
- be undertaken by an independent blinded auditor
- include hospital sites at which patients were admitted for the index admission and any related contiguous admission or related admission
- will include inpatient and hospital notes
- be audited cumulatively i.e. they will be checked for occurrence across the 26 week follow up period
- note the timing of items with reference to the index admission will be recorded
- occur at 6 month intervals

The Minimum Processes of Care are the following:

- patient assessed by allied health within 48 hours of admission
- Aboriginal Liaison Officer involved during inpatient stay
- language noted in medical file
- interpreter used if Aboriginal language is participant’s primary language
- telephone or face to face contact with family made by any allied health staff during inpatient stay
- Aboriginal brain injury educational resource provided during inpatient stay
- inpatient allied health service provided (any discipline)
- discharge plan developed with patient and family at family conference

- outpatient allied health service provided (any discipline)

In the case of participants returning from a metropolitan hospital to a regional/rural/remote location:

- verbal contact made by the metropolitan hospital with local rural service provider (hospital and local Aboriginal Medical Service)
- discharge report from metropolitan hospital sent to rural service provider (hospital and local Aboriginal Medical Service)

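### Section 16.4.2 collapses 9 to 11 partly conditional process-of-care items, one overlapping the intervention, into a single yes/no outcome, and fits a linear model to a service count

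*Protocol*

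**What the plan says.** **Processes of care.** Protocol Section 16.4.2 specifies a mixed effects logistic model. The outcome is defined thus: "The outcome variable will be a binary variable: minimum processes of care received by patient in the first 26 weeks post brain injury", with not received as the alternative. The hypothesis (Sections 2, 4.2 and 16.1) is increased compliance with the indicators.

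Section 10.4 lists nine processes. One is conditional on language: "interpreter used if Aboriginal language is" the participant's primary language. Two more follow under the condition "In the case of participants returning from a metropolitan hospital to a regional/rural/remote location". The number of applicable items therefore runs up to 11 and differs between patients. No section says how the items combine into received or not received.

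One of the nine is "Aboriginal brain injury educational resource provided during inpatient stay". The Synopsis describes the first intervention component as "Cultural Security Training for hospital staff surrounding brain injury, including culturally appropriate educational and treatment resources".

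**Occasions of service.** Section 16.4.2 states: "The outcome variable will be the count of the occasions of service in the first six months post brain injury". The model is linear with mixed effects, adjusted for injury type and severity, with time fixed and site random. For adverse events, the same section (Safety) expects a Poisson or negative binomial distribution and plans regression to match.

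**Labels.** Section 16.4.2 tags processes of care as H2a and occasions of service as H2b. Sections 2, 4.2 and 16.1 have them the other way round.

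**The concern.** Compliance is a matter of degree, and the file audit already records each process. A single yes/no variable discards that degree. Without an applicable-item denominator, it also treats alike patients who face different numbers of requirements. Its behaviour depends on an unstated rule: demanding rules push success towards zero and lenient ones towards 100%, and neither end measures compliance well.

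The educational-resource item adds a problem of interpretation. If one item is close to the intervention itself, and the composite requires every item, that item can drive the whole contrast. The trial could then report a large odds ratio for service delivery when the only change is that the intervention's own material was handed out.

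For occasions of service, the plan calls the outcome a count but models it as continuous, while choosing count models for adverse events. The likely cost is efficiency. Nothing is said about patients who die or withdraw before the six-month window closes.

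**Working it through.** The protocol gives no sample size, event rate or expected count for either H2 outcome, so there is no H2 figure to reproduce. Item rates, correlations and count distributions below are assumptions.

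**Patients per condition.** Four pairs of sites over six periods give 24 pair-periods. Control periods are 1 + 2 + 3 + 4 = 10 and intervention periods 5 + 4 + 3 + 2 = 14. From the total of 312 (Section 16.3), 312 × 10/24 = 130 control and 182 intervention patients.

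**1. Dependence on the combination rule.** With nine independent items each met with probability p, P(all) = p^9 and P(any) = 1 − (1 − p)^9.

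| p | P(all nine) | expected among 130 controls |
|---|---|---|
| 0.60 | 1.0% | 1.3 |
| 0.70 | 4.0% | 5.2 |
| 0.80 | 13.4% | 17.4 |
| 0.90 | 38.7% | 50.4 |

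At p = 0.70, P(any) = 1 − 0.3^9 = 99.998%. With eight items (interpreter not applicable), P(all) at 0.70 is 5.8%; with eleven it is 2.0%.

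Independence is a strong assumption. Under a beta-binomial with between-item correlation 0.3, P(all) = ∏(a + i)/(t + i) for i = 0 to 8, with t = 0.7/0.3 = 2.333 and a = 2.333p. At p = 0.70 this gives 26% for all and 98% for any. The spread narrows but remains large.

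**2. Information lost.** Take a 10-point rise in every one of nine items, a two-sided 5% test and 130 against 182 patients, ignoring clustering and period effects. The score is the proportion of items met, with SD = √{mean of p(1 − p) × (1 + 8 × 0.3)/9}. For 60% to 70% this is √(0.225 × 3.4/9) = 0.292.

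| item rate | all-items, independent | all-items, correlation 0.3 | score, correlation 0.3 |
|---|---|---|---|
| 60% to 70% | 0.35 | 0.61 | 0.85 |
| 70% to 80% | 0.82 | 0.84 | 0.91 |
| 80% to 90% | 0.999 | 0.99 | 0.98 |

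The last two columns compare like with like. The loss is material at low item rates and disappears at high ones.

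**3. The overlapping item.** Let only the resource item change, from q in control to 80% under intervention, with the other eight fixed at p. Under an all-items rule, success is p^8 × q against p^8 × 0.8. For p = 0.80 and q = 0.05: 0.1678 × 0.05 = 0.0084 against 0.1678 × 0.8 = 0.1342, so the odds ratio is (0.1342/0.8658)/(0.0084/0.9916) ≈ 18.3.

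| q in control | odds ratio, other items 70% / 80% / 90% |
|---|---|
| 5% | 16.7 / 18.3 / 23.9 |
| 20% | 4.1 / 4.5 / 5.6 |
| 0% | no control successes; not estimable |

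On a proportion-of-items score, the same change from 5% to 80% moves the mean by 0.75/9 = 0.083.

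**4. Linear against count model.** Simulation, 400 runs per setting; control mean 20 sessions, negative binomial counts, follow-up shortened in 10% of both conditions. The comparator is a negative binomial model with a log-exposure offset.

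| dispersion | linear type I error | linear power, rate ratio 1.4 | negative binomial power |
|---|---|---|---|
| 0.5 | 0.045 | 0.455 | 0.562 |
| 1 | 0.040 | 0.250 | 0.310 |
| 2 | 0.032 | 0.142 | 0.155 |

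The gains are 10.7, 6.0 and 1.3 points. With equal rates but follow-up shortened in 15% of control and no intervention patients, the linear model rejected in 0.080 of runs, with a mean shift of +1.6 sessions; the offset model rejected in 0.068.

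**The case against.** The strongest reply is that Section 16.4.2 never says all items must be met. The combination rule and the treatment of non-applicable items could stand in a statistical analysis plan that is not shown, and an all-or-none measure can be legitimate once defined. That stands as far as it goes: the 4% is one reading, not the plan's stated rule. It does not remove the point, because the reduction to one binary variable is fixed in the protocol itself and fits poorly with a hypothesis about increased compliance.

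Three stronger readings are tempting, and the documents do not support them.

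- *That control success is zero by construction and the odds ratio cannot be estimated.* This needs both an all-items rule and a resource that is absent in control periods. Neither is stated. The introduction (Section 3) reports too little accessible information and too few culturally appropriate resources, which makes low control rates plausible, but that is inference. The overlap is one item in 9 to 11.
- *That the linear model gives badly calibrated intervals.* Skewness is not stated, and the simulated type I error was 0.032 to 0.045. A mean difference in sessions is a valid target.
- *That patients have unequal time at risk.* The window is nominally six months for everyone, counts come from files and administrative systems (Section 10.4), and patients unlikely to survive to 26 weeks are excluded (Section 7.2.2). Shortened observation arises only through death or withdrawal, for which no rates are given.

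It is also fair that an observed-time offset is not a neutral correction. It changes the target to a rate, and if sessions cluster in the inpatient stay, an early death yields a high rate.

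**Conclusion.** The concern holds in limited form. The binary process-of-care outcome lacks an applicable-item denominator and can land near either end of its range, depending on a rule the protocol does not give. Under an all-items reading, the overlapping item alone can produce an odds ratio of about 4 to 24 over the control rates of 5% to 20% examined. An applicable-items analysis is more informative at low item rates (power 0.85 against 0.35 to 0.61 for a rise from 60% to 70%) and no better at high ones. These figures rest on assumed item rates and correlations and ignore clustering.

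The linear model for occasions of service is a question of efficiency and consistency, not validity: roughly 1 to 11 points of power under assumed overdispersion, the smallest gain being within simulation error. The label swap is editorial, since each outcome is named in words. Both outcomes are secondary; the primary analysis and the 312 are untouched. The changes should be made before database lock.

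**What to change.** - **Compliance:** analyse applicable items met per patient, by a binomial or item-level logistic mixed model with item and period fixed effects and patient and cluster random effects. State which items apply to whom. Keep any all-or-none result as descriptive, with its rule written down.
- **Educational resource:** report this item separately as intervention fidelity, and give the compliance analysis with and without it.
- **Occasions of service:** use a negative binomial mixed model with the same period, cluster, injury type and severity terms.
- **Death and withdrawal before 26 weeks:** state the handling for both outcomes. Use an observed-time offset only as a sensitivity analysis, because it changes the estimand to a rate.
- **Labels:** align H2a and H2b in Section 16.4.2 with Sections 2, 4.2 and 16.1.

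The cost is wording in the protocol or analysis plan and some programming. The audit in Section 10.4 already covers the individual processes, so no new data are needed.
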